	
 
Proteinuria > 0.5 g/day quantified from 24-hour urine collection or urine protein:creatinine ratio >50 mg/mmol or urine albumin:creatinine ratio >30 mg/mmol
 
Clinic systolic BP >130 mmHg or diastolic BP >85 mmHg (automated office BP measurement)
 
Willing to self-manage BP
 

Exclusion criteria	Any of the following:
	Currently receiving immunosuppression or in need of urgent start immunosuppression (e.g., rapidly progressive glomerulonephritis or nephrotic syndrome)
	
 
Kidney failure defined by the need for dialysis, kidney transplantation or eGFR <15 mL/min
 

	Recent (within 3 months) history of acute myocardial infarction or stroke
	Heart failure with reduced ejection fraction
	Concomitant diabetic nephropathy on kidney biopsy
	Pregnancy (or actively planning a pregnancy) or breastfeeding
	Life expectancy <12 months
	Allergy or intolerance to both an angiotensin converting enzyme
	inhibitor and angiotensin II receptor blocker
	Severe hypertension (>180/100 mmHg)
Treatments	Intervention arm (study treatment)
	Self-management of BP including self-monitoring of home BP values and self-titration of medications according to a pre-specified individualized
	treatment plan
	Control arm
	Usual management of BP and anti-hypertensive therapy by a physician at regularly scheduled clinic visits
Sample size pilot trial	Target recruitment: 25 patients over 2 years across three sites (The Ottawa Hospital Glomerulonephritis Clinic and the Glomerulonephritis Clinic in Vancouver General Hospital and St. Paul's Hospital, Vancouver)
	Justification: The target sample size is primarily based on the incidence of
	IgA nephropathy and the anticipated recruitment rate from the clinic. We
	will seek to recruit newly diagnosed patients but will also include prevalent
	patients at each site. The target sample size should be sufficient to address
	practical questions regarding the feasibility of conducting a larger clinical
	trial with respect to recruitment, ease of implementation of the intervention,
	and collection of efficacy and safety outcomes. The total sample size of 25
	participants is further supported by a sample size calculation for the
	participanto is further supported by a sample size calculation for the

	feasibility metric of retention of participants in the trial. The progression criterion for this outcome is 80%. Assuming 90% of participants complete

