# 2. Study objectives and research questions

# 2.1 Primary objective of SMART-IgAN pilot

To determine the feasibility of a full-scale trial by showing that self-management of blood pressure is acceptable to patients and achievable in the clinic setting.

Hypothesis: At least 50% of eligible patients will be randomized; at least 80% of participants will complete the study.

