# 3. Outcomes

# 3.1 Primary outcome

The primary outcome of the pilot trial will be feasibility defined as achieving target threshold for both recruitment and study completion. The study protocol will be revised based on adherence metrics and participant feedback as detailed below:

- 1. The probability of successful recruitment will be calculated as the percentage of eligible participants who are randomized. A threshold of >50% will be required for progression to a full-scale trial.
- 2. The probability of retention will be calculated as the percentage of randomized patients who complete the study. A threshold of >80% will be sought for progression to a full-scale trial.
- 3. Adherence to the self-management protocol will be quantified for each patient in the intervention group using the median number of recorded home BP readings per measurement week. Adherence will be further explored from participant feedback in longitudinal diary entries and a semi-structured interview. Fidelity of the intervention will also be explored retrospectively by comparing the submitted BP readings to the BP readings downloaded from the machine at the end of the study period. There is no progression criterion for adherence but the study protocol for a future full-scale trial will be refined based on these factors.

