# 12. Analysis plan

# 12.1 Sample size justification

IgAN is the most common condition treated in the Glomerulonephritis Clinic at both sites. Approximately 30 individuals are diagnosed with IgAN on a kidney biopsy each year in Ottawa. Over the course of 2 years, we anticipate that half of these patients (30 out of 60) would be eligible for the trial, and we are seeking to recruit at least 50% of eligible patients (n=15). The Glomerulonephritis Clinic at Vancouver General Hospital has a larger patient population and we are seeking to recruit 10 patients from that site.

The total sample size of 25 participants is supported by a sample size calculation for the feasibility metric of retention of participants in the trial. The progression criterion for this outcome is 80%. Assuming 90% of participants complete the 6-month study duration, a total of 26 participants would be needed to provide a one-sided 95% confidence interval of 10% (i.e. a lower bound estimate of 80%).

For a definitive trial, a sample size of 186 patients would provide 80% power to detect a between-group mean difference in systolic BP of 7 mmHg (a more conservative effect size compared to TASMIN-SR) assuming a standard deviation of 17 mmHg.

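### The recruitment progression criterion measures uptake among eligible patients and ignores accrual volume, so a pass says nothing about whether 186 patients can be reached

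*Protocol*

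**What the plan says.** Section 3.1 makes the primary outcome "feasibility defined as achieving target threshold for both recruitment and study completion". The recruitment part is defined as follows: "The probability of successful recruitment will be calculated as the percentage of eligible participants who are randomized". It then states: "A threshold of >50% will be required for progression to a full-scale trial". The synopsis repeats this rule, and the hypothesis in section 2.1 has the same form: "At least 50% of eligible patients will be randomized; at least 80% of participants will complete the study". The only other progression criterion is retention; adherence has no threshold.

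A count and a period do appear in the protocol, but only as planning figures. The synopsis gives "Target recruitment: 25 patients over 2 years across three sites". Section 12.1 splits this into 15 from Ottawa and 10 from Vancouver. The Ottawa figure starts from incident cases: "Approximately 30 individuals are diagnosed with IgAN on a kidney biopsy each year in Ottawa", and then "Over the course of 2 years, we anticipate that half of these patients (30 out of 60) would be eligible for the trial". The synopsis adds that the team "will seek to recruit newly diagnosed patients but will also include prevalent" patients.

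The full-scale trial is put at 186 patients in the synopsis and section 12.1, with no number of sites and no accrual period. The synopsis entry on expected outcomes says the pilot will establish that the larger trial is feasible as regards recruiting patients.

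**The concern.** A ratio of randomized to eligible patients answers one question: of those who could join, how many do? It does not answer how many patients a site can supply per year. A full-scale trial needs both answers. The synopsis bases the pilot's size mainly on disease incidence and the expected recruitment rate, so patient supply is recognised as a constraint, yet it is left out of the test.

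If the rule is followed as written, a pilot that accrues far below plan is declared feasible as long as enough of the few eligible patients agree and most of them complete. The figure needed to plan 186 patients, the rate per site-year, then has no bearing on the decision to proceed.

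**Working it through.** **Inputs.** Rule: randomized / eligible > 50%, and completers / randomized > 80% (section 3.1). Planned accrual: 25 in 2 years at three hospitals (synopsis). Full-scale size: 186, for a difference of 7 mmHg, SD 17 mmHg and 80% power (section 12.1).

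**1. Reproduce 186.** Assume two-sided 5% alpha, 1:1 allocation and no allowance for dropout, none of which is stated for the full-scale trial. Per arm, n = 2 × (1.960 + 0.842)² × 17² / 7² = 92.6, rounded up to 93, so 186 in total. The figure reproduces. Keeping the pilot's 2:1 allocation would give 210 instead.

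**2. Does the rule depend on volume?** The following results over 2 years are hypothetical. The last column applies 186 / (randomized per year) to the pilot hospitals alone.

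| Randomized / eligible | Uptake | Passes > 50%? | Share of 25 | Per year | Years to 186 |
|---|---|---|---|---|---|
| 6 / 10 | 60% | yes | 24% | 3.0 | 62.0 |
| 9 / 16 | 56% | yes | 36% | 4.5 | 41.3 |
| 11 / 20 | 55% | yes | 44% | 5.5 | 33.8 |
| 16 / 30 | 53% | yes | 64% | 8.0 | 23.3 |
| 25 / 50 | 50% | no | 100% | 12.5 | 14.9 |

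In the 9 of 16 case, 8 of 9 completing is 89%. Both thresholds are then met and the pilot is declared feasible. The last row shows the reverse: accrual fully on target misses a strict > 50%. Section 12.1 expects 15 of 30 in Ottawa, which is exactly 50%.

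**3. What the planned rate implies for 186.** Planned rate: 25 / 2 = 12.5 per year, and 12.5 / 3 = 4.17 per hospital per year.
- At the pilot hospitals alone: 186 / 12.5 = 14.9 years.
- Assumed 3-year accrual: 186 / 3 = 62 per year; 62 / 4.17 = 14.9, about 15 sites (5.0 times the pilot rate).
- Assumed 5-year accrual: 186 / 5 = 37.2 per year; 37.2 / 4.17 = 8.9, about 9 sites (3.0 times the pilot rate).

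Section 12.1 speaks of two sites. Counting two centres gives 12.5 / 2 = 6.25 per centre per year, and then 62 / 6.25 = 9.9 and 37.2 / 6.25 = 6.0, so about 10 and 6 centres.

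**4. Would a hard cut-off at 25 work?** Assume Poisson accrual whose true mean equals the plan. The chance of fewer than 25 when the mean is 25 is about 47%. Requiring both 15 in Ottawa and 10 in Vancouver would fail about 71% of the time. A fixed cut-off at the target would therefore reject many pilots that are running to plan.

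**The case against.** The percentage fits the objective in section 2.1, which is about acceptability to patients and achievability in clinic. Uptake also carries over to new sites better than a local count does. This stands, and is the reason to keep the percentage.

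Slow accrual would not go unseen. Section 9.4 puts recruitment data in the DSMB interim report, section 11.1 has the Project Office follow up centres with recruitment problems, and section 11.3 has the steering committee meet every 6 months. Nor does section 3.1 say that progression is automatic once the threshold is met. This also stands, but none of that monitoring feeds into the definition of feasibility, which is the primary outcome.

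Three stronger readings are tempting and not supported:
- A reader might infer that the 186-patient trial cannot be filled. The protocol gives neither the number of sites nor the accrual period for that trial and does not confine it to the pilot hospitals, so the figures in years are a same-sites illustration.
- A reader might infer that too few eligible patients is the likeliest way for the trial to fail. Section 12.1 calls IgAN the commonest condition treated in these clinics and expects 30 eligible incident patients in Ottawa alone; 9 of 16 is a constructed case.
- A reader might infer that enrolling prevalent patients must inflate the observed rate. The Ottawa target is derived from incident cases only, new sites may bring prevalent patients of their own, and the eventual mix is unknown. That supports separate reporting, not a conclusion of bias.

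**Conclusion.** The point holds for the progression criterion, not for the protocol as a whole, which does state an accrual target. As written, the rule is indifferent to volume: results at 24% to 64% of the planned 25 all pass. That finding needs no assumption beyond the text of section 3.1. The site and year figures do rest on assumptions: equal accrual per hospital, an accrual period of 3 to 5 years, and 186 taken without dropout inflation. Participant safety and the pilot's data are unaffected. What is affected is whether half of the primary outcome can answer the recruitment question the synopsis sets for it. The change is worth making before results are known.

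**What to change.** In section 3.1 and the synopsis, keep the uptake percentage and add a second recruitment component:

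- The number randomized per site-year, judged against the plan's own 25 in 24 months (4.2 per hospital per year if three hospitals are counted).
- Three zones fixed before results are known: proceed; proceed with changes, such as more sites; do not proceed. The boundaries should leave room for chance, so that accrual truly at plan seldom falls in the lowest zone. A hard cut-off at 25, or at 15 and 10 by site, should be avoided.
- The rate reported separately for newly diagnosed and prevalent patients.
- A statement of the number of sites and years the observed rate implies for 186.

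The hypothesis in section 2.1 should be brought into line. The cost is protocol wording, with no new visits, participants or assessments. Biopsy date must be taken from the chart, since it is not among the items listed for the baseline CRF, and each site's opening date must be logged to give site-years. The downside is that slow accrual can then block or qualify progression.

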### 3.2 Secondary outcomes

The main secondary outcome of the pilot trial will be patient experience of self-management. This will be captured longitudinally during the trial in a monthly diary entry and at the end of the trial via a 1:1 semi-structured interview.

Efficacy outcomes will be assessed on an exploratory basis only:

- 1. Mean difference in achieved BP between the groups at the end of the study period (primary efficacy outcome in a future full-scale trial)
- 2. Difference in systolic BP from baseline to 6-month follow-up (using an automated office BP measurement)
- 3. Difference in diastolic BP from baseline to 6-month follow-up (using an automated office BP measurement)
- 4. Difference in percentage proteinuria reduction between the groups from baseline to 6 months (key secondary outcome in a future full-scale trial)
- 5. Proportion of patients who achieve an absolute reduction in proteinuria to less than 0.5 g/day at the 6-month visit
- 6. Change from baseline in exercise, 24-hour urinary sodium excretion (surrogate for dietary salt intake) and waist circumference at the 6-month visit

### Safety outcomes:

- 1. Orthostatic hypotension (measured at clinic visits)
- 2. Change in estimated glomerular filtration rate (eGFR) during the study period
- 3. Hyperkalemia episodes (serum potassium >5.3 mmol/L)
- 4. Frequency of coordinator intervention required in the self-management arm due to protocol deviations/errors

### 4. Trial design

### 4.1 Setting and Participants

SMART-IgAN is a pilot, unblinded, randomized controlled trial of self-management of blood pressure versus usual care in patients with IgA nephropathy attending Glomerulonephritis (GN) clinics at The Ottawa Hospital, Ottawa, Ontario, and in Vancouver, British Columbia (Vancouver General Hospital and St. Paul's Hospital).

# 4.2 Study duration

Participants will be followed for 6 months and will have three dedicated study visits embedded within their regularly scheduled clinic visits at baseline (day of randomization), 3 months and at 6 months (study completion). Outcomes will be assessed at the 6-month mark.

# 4.3 Randomization and allocation process

Randomization will be 2:1 intervention-to-control, and will be carried out with a web-based randomization system. A 2:1 allocation was chosen because there is already extensive experience of the usual care arm of the trial, and the intent is to determine the acceptability and safety profile of the intervention. The randomization website will be managed by the Data Management Services of the Ottawa Methods Centre Ottawa Hospital Research Institute. Randomization will be stratified by site (Ottawa versus Vancouver).

# 4.4 Blinding and protection against bias

SMART-IgAN will be an open-label trial as there is no way to blind participants or investigators due to the nature of the intervention. The primary efficacy outcome is the achieved systolic BP which will be measured using an automated office BP measurement with the participant left unattended in the room. This is an objective measure that would not be influenced by knowledge of the intervention.

# 5. Study population

The target population for SMART-IgAN includes adult patients with a diagnosis of IgA nephropathy confirmed on a kidney biopsy and suboptimal BP control. Potential participants at The Ottawa Hospital will be identified using (i) an existing registry of patients who have biopsy-confirmed IgA nephropathy (the Ottawa GN database) and/or (ii) a clinic planner (a Word document that is completed by a physician prior to the clinic that lists the patients attending the clinic on a specific day and includes information about their underlying diagnosis and a summary of their care plan). The Ottawa GN database is housed within the Ottawa Hospital Research Institute (OHRI) and is

password protected. The clinic planners are housed in a folder on SharePoint and are only accessible to physicians, nurses and administrative staff who work in the GN clinic.

Clinic patients who are potentially eligible for recruitment will be contacted by phone outside of their regularly scheduled clinic visit by either a healthcare professional within their circle of care or by a research coordinator. Patients who indicate a willingness to participate in the study will be offered the opportunity to read the consent form prior to their in-person clinic visit, at which time full eligibility will be determined based on their BP value in the clinic. Patients who meet all inclusion criteria will be consented and randomized on the same day as their scheduled clinic visit. If this is not feasible (for example due to time constraints), they will be offered an alternative date to return to the clinic for completion of the consent form.

Individuals who decline to participate will be asked if the following information may be collected so that the investigators can compare individuals who complete the study to those that elect not to participate: (i) reason(s) for not wishing to participate; (ii) demographic characteristics (sex, decade of age); (iii) clinical characteristics (level of kidney function, degree of proteinuria, clinic blood pressure value).

### 5.1 Inclusion criteria

- Adult patients aged ≥18 years who provide written informed consent.
- Biopsy-confirmed diagnosis of IgAN.
- Proteinuria > 0.5 g/day quantified from 24-hour urine collection or urine protein:creatinine ratio >50 mg/mmol or urine albumin:creatinine ratio >30 mg/mmol.
- Clinic systolic BP >130 mmHg or diastolic BP >85 mmHg (automated office BP measurement)
- Willing to self-manage BP

#### 5.2 Exclusion criteria

- Currently receiving immunosuppression or in need of urgent start immunosuppression (e.g., rapidly progressive glomerulonephritis or nephrotic syndrome).
- Kidney failure defined by the need for dialysis, kidney transplantation or eGFR
   <15 mL/min.

- Recent (within 3 months) history of acute myocardial infarction or stroke.
- Heart failure with reduced ejection fraction.
- Concomitant diabetic nephropathy on kidney biopsy.
- Pregnancy (or actively planning a pregnancy) or breastfeeding.
- Life expectancy <12 months.
- Allergy or intolerance to both an angiotensin converting enzyme inhibitor and angiotensin II receptor blocker.
- Severe hypertension requiring urgent treatment (>180/100 mmHg).

### 5.3. Use of SGLT2 inhibitors

The use of SGLT2 inhibitors has become more widespread in IgAN based on findings from recent large clinical trials, which included a sizeable number of participants with chronic kidney disease secondary to IgAN. Although there is strong evidence to support their use in the long-term management of IgAN, their precise role in the shortterm after biopsy diagnosis is not clear especially for patients who are candidates for immunosuppression. Additionally, access to these medications is not uniform across Canada for patients who do not have diabetes. Variable use of SGLT2 inhibitors would likely lead to unbalanced co-interventions with a greater likelihood that a SGLT2 inhibitor would be started in the control group due to persistent proteinuria from suboptimal BP control and/or slower titration of RAAS inhibition. To overcome this potential limitation, patients who have already been started on a SGLT2 inhibitor will be allowed to enter the trial as long as they have been on stable doses for at least 4 weeks and the dose is not titrated during the 6-month follow-up period. Patients who are not receiving a SGLT2 inhibitor at the time of randomization will not be prescribed the medication until they have completed the 6-month trial period. For a future full-scale trial, randomization will be stratified on SGTL2 inhibitor use at baseline to ensure that it

is balanced between intervention and control groups. This approach was taken in a recent trial of semaglutide in patients with chronic kidney disease.

# 6. Participant withdrawal and study discontinuation

# 6.1 Withdrawal of participants

Study participants will be followed until either the final study visit at 26 weeks. A participant may withdraw consent from the study at any time and for any reason. If a participant withdraws consent, they will be withdrawn from the trial. Participants will be assured that their withdrawal from the trial will not in any way affect the on-going management of their kidney condition (as would have been done had the patient not entered the study). The decision of an investigator to withdraw a study subject will be based on any or all of the following:

- i) Any clinical adverse event, safety concerns, laboratory abnormality, or other medical condition or situation occurs such that continued participation in the study would not be in the best interest of the participant
- ii) It is in the participant's best interest according to the Investigator's clinical judgment
- iii) The participant meets an exclusion criterion (either newly developed or not previously recognised) that precludes further study participation
- iv) The study is prematurely terminated

If a participant withdraws consent for further study follow-up procedures and assessments, every effort will be made to continue to follow the participant for their safety and vital status outcomes. Consent for collection of any adverse events as well as their clinical and biological data will be sought by the research team. The participant will be asked if they wish to:

- i) Withdraw from study intervention/treatment only and agree to be followed at study visits as stipulated in the protocol/consent form; OR
- ii) Withdraw from study intervention/treatment and permit follow-up by phone or review of clinic/hospital records for data collection and vital status; OR

- iii) Withdraw from study intervention/treatment and decline further contact however permit data obtained to date to be included in the analysis; OR
- iv) Withdraw from study intervention/treatment, decline further contact and access to personal health information and indicate data collected to date cannot be used in the final analysis.

Subjects who are withdrawn will not be replaced. Source documents will not be destroyed until completion of the long-term storage period.

The primary reason for premature withdrawal and the participant's decision to decline study follow-up will be recorded in the participant's source documents and related case report form (CRF). If a withdrawal is a result of a serious adverse event, the conditions will be clearly documented and reported to the research ethics board (REB). If withdrawal is a participant's decision due to concerns about the use of their personal health information, these will be reported to the REB and the privacy office. If withdrawal is a participant's decision due to concern about their rights, safety, or wellbeing, the participant will be instructed to contact the REB at the number listed in the informed consent form. Additionally, the REB will be contacted by the study team to discuss the participant's concern.

Major deviations from the trial treatments or cessation of medications by the patient do not require withdrawal of the participant; these patients shall remain in the study and followed up until the end of the study (except where the participant withdraws consent).

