### 1.2 How can a reduction in proteinuria be achieved?

Although immunosuppression treatment is available for patients with IgAN, it comes with a risk of serious infections and is therefore typically reserved for high-risk patients (defined as the presence of persistent high-grade proteinuria, usually ≥1 g/day). Consideration for immunosuppressive treatment is determined after an observational period of approximately 6 months following diagnosis via kidney biopsy, during which time patients receive non-immune or "supportive" therapy. The cornerstone of supportive therapy in IgAN is blood pressure (BP) control through the use of renin angiotensin aldosterone system (RAAS) inhibitors which have been shown to reduce proteinuria and improve kidney outcomes in non-diabetic patients with proteinuria, 10 including patients with IgAN. 11,12 In prospective studies, with BP management alone, up to 50% of patients with IgAN can achieve partial or complete remission of their disease based on a reduction in proteinuria. Since IgAN is a chronic disease, supportive care

needs to be maintained throughout the patient's illness trajectory, irrespective of the decision to pursue short courses of immunosuppression.

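### Section 6.1 gives no follow-up route for participants whom the investigator withdraws, so 6-month data can be lost for outcome-related reasons and the retention count lowered

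*Protocol*

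**What the plan says.** Section 6.1 introduces the investigator's grounds with "The decision of an investigator to withdraw a study subject will be based on any or all of the following". The object of the decision is the subject's place in the study, not only the intervention. Ground (i) covers adverse events, safety concerns, laboratory abnormalities and other medical conditions that make continued participation not in the participant's interest. Ground (ii) is clinical judgment of best interest. Ground (iii) reads "The participant meets an exclusion criterion (either newly developed or not previously recognised) that precludes further study participation".

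Section 5.2 supplies the criteria to which ground (iii) refers. Those that could newly arise in six months include "Currently receiving immunosuppression or in need of urgent start immunosuppression (e.g., rapidly progressive glomerulonephritis or nephrotic syndrome"), "Severe hypertension requiring urgent treatment (>180/100 mmHg"), "Kidney failure defined by the need for dialysis, kidney transplantation or eGFR" below 15 mL/min, a recent myocardial infarction or stroke, and intolerance to both RAAS inhibitor classes.

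Three provisions deal with follow-up after something goes wrong:

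- Section 6.1 promises continued follow-up for safety and vital status, and lists four options, the first being to leave the intervention but keep attending study visits. The paragraph opens with the participant withdrawing consent.
- Section 6.1 later says of participants with major treatment deviations or stopped medication that "these patients shall remain in the study and followed up until the end of the study".
- Section 6.2 covers participants who are being lost to follow-up or who leave voluntarily.

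Withdrawn subjects are not replaced (section 6.1). Retention is the percentage of randomized patients who complete the study (section 3.1).

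**The concern.** A participant whom the investigator withdraws falls between these provisions. Read as written, that person leaves the study before the 6-month BP, 24-hour urine and laboratory assessments, although the scheduled clinic visits would have been available for collecting them.

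The loss is unlikely to be random. Severe hypertension, falling eGFR and hyperkalemia either are the trial's efficacy and safety outcomes or lie close to them. Intolerance to both RAAS inhibitor classes concerns the drugs being titrated. The protocol also expects the arms to differ in relevant ways: section 5.3 foresees more persistent proteinuria in controls, and section 9.1 foresees a possibly higher risk of adverse events in the intervention arm from faster escalation. In an open-label trial, withdrawals at discretion could therefore differ by arm in number and in reason.

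Two things are at stake. One is the completeness of the exploratory efficacy data and of the safety data. The other is the retention figure, part of the primary feasibility outcome, which would mix investigators' decisions with participants' own. A statistical analysis plan cannot repair the first, because the data would not have been collected.

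**Working it through.** **Who is kept in follow-up**

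| Event | Provision | Follow-up stated? |
|---|---|---|
| Participant withdraws consent | 6.1, effort to follow and four options | Yes, to the extent the participant agrees |
| Major treatment deviation, or patient stops medication | 6.1, later paragraph | Yes, to end of study |
| Missed visits or voluntary early exit | 6.2 | Contact attempts; permission to use data |
| Investigator withdraws under (i) to (iii) | None | No |

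The loss of outcomes in the last row is inferred from the wording and from the missing provision. The protocol does not state it outright.

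**The plan's own retention figure**

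Inputs from section 12.1: expected completion 90%, lower bound 80%, one-sided 95%. The simple normal-approximation formula gives n = 1.645² × 0.9 × 0.1 / 0.1² = 24.35, so 25. The stated figure is 26. The lower bound is 80.1% at n = 25 and 80.3% at n = 26, so the plan's figure is reproduced to within one participant.

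**The pass mark**

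- N = 25, above 80% (section 3.1): 21/25 = 84% passes and 20/25 = 80% fails. At most 4 may be lost.
- N = 25, at least 80% (hypothesis in section 2.1): 20/25 = 80% passes and 19/25 = 76% fails. At most 5 may be lost.
- N = 26, either wording: 21/26 = 80.8% passes and 20/26 = 76.9% fails.

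Each withdrawal at N = 25 costs 1/25 = 4 percentage points. With 2:1 allocation the arms hold about 17 and 8, so one lost control is about one eighth of that arm's 6-month data. Expected losses at 90% completion are 0.10 × 25 = 2.5.

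**How sensitive the decision is**

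The documents give no rate for these withdrawals, so the counts below are assumptions. Suppose k of 25 participants are withdrawn by the investigator and each of the rest completes with probability 0.9. The chance of passing is the binomial probability that 25 − k participants yield at least 21 (or 20) completers.

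| k | Above 80% (21 needed) | At least 80% (20 needed) |
|---|---|---|
| 0 | 0.90 | 0.97 |
| 1 | 0.79 | 0.91 |
| 2 | 0.59 | 0.81 |
| 3 | 0.34 | 0.62 |

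Rows 1 to 3 apply only if the 90% excludes investigator withdrawals. If it is all-cause completion, these withdrawals are already inside the 10%, and the first row is the planned position.

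**The case against.** Much of the opposing case stands, and it limits what can be claimed.

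- A reader might infer that anyone who newly meets an exclusion criterion is removed. The text does not say so. The decision is discretionary, and ground (iii) is confined to criteria that preclude further participation. That qualifier is undefined, however, and section 5.2 does not say which criteria meet it.
- A reader might infer that every trigger results from poor BP or proteinuria control. The documents do not support that. The examples of urgent immunosuppression are rapidly progressive disease and nephrotic syndrome, and myocardial infarction and stroke are not attributed to BP control in the trial. The BP criterion also requires urgent treatment, and section 7.1.1 handles persistent home readings above 180 mmHg systolic with a call to the clinic.
- The non-urgent immunosuppression decision is a weak example. Section 1.2 says "Consideration for immunosuppressive treatment is determined after an observational period of approximately 6 months following diagnosis via kidney biopsy". For newly diagnosed patients that is largely at or after the end of follow-up; prevalent patients could reach it sooner.
- The stay-in-study sentence might look like a contradiction. It has a different trigger, so it is not one. It shows only that the protocol already knows how to keep someone under follow-up off treatment.
- It is tempting to say that two further withdrawals on top of the expected losses turn a pass into a fail. With 2 + 2 = 4 losses, 21/25 still passes. With 3 + 2 = 5 losses, 20/25 fails only under the section 3.1 wording. The sum may also count the same people twice, since the 90% refers to completing the study without separating reasons.
- Counting safety withdrawals as non-completion is a defensible feasibility measure. Section 2.1 asks whether the intervention is achievable in the clinic as well as acceptable to patients. Section 6.1 already requires the primary reason for withdrawal to be recorded, so the two kinds can be told apart.
- Efficacy outcomes are exploratory (section 3.2), so no confirmatory inference is at risk in this pilot.

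None of this supplies the missing follow-up provision.

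**Conclusion.** The point holds as a gap in section 6.1: no provision keeps an investigator-withdrawn participant in follow-up, and some of the possible triggers are related to the outcomes or to the drug class being titrated. The rule can therefore cause informative loss of exploratory efficacy data and of safety data.

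The effect on retention is mechanical: 4 percentage points per participant, against an allowance of 4 or 5 losses depending on which threshold wording governs. Whether it would change the progression decision cannot be said from the documents, because the event rate is not given and the 90% may already include such cases. The scenario probabilities show sensitivity and are not a forecast.

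The consequence is modest for this pilot. It would weigh more if the same wording passed into the full-scale trial, where achieved systolic BP is the primary outcome and proteinuria the main secondary one. The correction is cheap enough to make now.

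**What to change.** In section 6.1, separate two decisions: stopping the study intervention and leaving the study. State that a participant whose intervention the investigator stops under grounds (i) to (iii) remains in follow-up at the scheduled week-12 and final visits, with the BP, urine, laboratory and adverse event assessments planned there, unless the participant withdraws consent. The simplest drafting extends the first of the four existing options to investigator-initiated withdrawal. When the intervention stops remains the investigator's decision.

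Report investigator-stopped and participant-withdrawn cases separately beside the retention count, and state whether an investigator-stopped participant who attends the final visit counts as a completer. Sections 2.1 and 3.1 should use the same threshold wording, so that 20 of 25 has one reading.

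The cost is a short protocol amendment and attendance by a few participants at clinic visits already scheduled. The downside is that some 6-month outcomes will be measured off intervention.
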